9.2 Serious Adverse Event (SAE)

A serious adverse event (SAE) will be those signs, symptoms, illnesses, abnormal or adverse laboratory values, or experiences that were not present at the start of treatment and occurs, or worsens during the course of therapy and has one of the following outcomes:

- Death
- Is life-threatening
- Requires inpatient hospitalization or prolongation of existing hospitalization
- Results in persistent or significant disability/incapacity
- A congenital anomaly/birth defect
- Requires medical or surgical intervention to prevent permanent impairment or damage

9.3 Reporting of Adverse Events

With each visit, the patient provider will assess the patient for AE since prior visits. Providers will directly ask about adverse events and record their occurrence, as well as those that are offered voluntarily by the participant.

Events will be documented to include:

- The participant's identification, disease and stage, cycle and day of treatment when AE occurred (if applicable)
- Time of onset
- Duration
- Severity by grade (per CTCAE Version 5.0),
- A brief description of the event
- Drug, device, or intervention suspected of causing the event
- Contributing factors, if applicable
- Action taken to intervene
- Time of resolution, or
- If the AE is ongoing at the conclusion of participation in the study
- Laboratory values will be included as adverse events if clinically significant and included in reporting.

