3.0 Study Design

This is a multi-center, phase II study investigating the efficacy of total neoadjuvant therapy with mFOLFOX and short course radiation and selective non-operative management in patients with locally advanced rectal cancer.

Participants with Stage IIA, IIIA, IIIB rectal adenocarcinomas, except for any T4 or N2b disease, who would otherwise undergo long course concurrent chemotherapy and radiation therapy followed by TME may be enrolled for treatment with mFOLFOX therapy. Participants with lower sphincter rectal cancer deemed not eligible for sphincter sparing surgery are not eligible for participation. Participants would be treated with up to 12 cycles of mFOLFOX therapy. (One cycle of mFOLFOX= 14 days) and short course radiation.

All patients will be evaluated once following six cycles of chemotherapy via endoscopy and CT plus MRI.

Patients with a partial, near or complete response will receive an additional 4-6 cycles of chemotherapy followed by reassessment.

Patients with stable or progressive disease defined as less than 20% reduction will be removed from study.

Following completion of all chemotherapy (10-12 cycles) patients will be re-assessed via endoscopy and CT plus MRI. Patients will then receive short course radiation followed by repeat assessment with endoscopy and CT/MRI. Those patients with evidence of complete or near complete clinical response following completion of all chemotherapy and radiation will be treated non-operatively and undergo close surveillance.

Patients with a partial response or stable disease will undergo TME.

Those with <20% response will be removed from study and undergo treatment per the treating investigator. These patients will be followed for survival at six month intervals for up to 5 years.

All patients will be followed for 5 years following last date of treatment:

- For patients in the study not requiring surgery following chemotherapy, the last day of treatment will be considered the last day of mFOLFOX therapy.
- For patients who receive short course radiation, the last day of treatment will be considered the last day of radiation.
- For patients in the TME group, the last day of treatment will be considered the day of surgery.

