9.0 Adverse Events Monitoring and Reporting

9.1 Definition of Adverse Event (AE)

Adverse events (AE) will be defined as any sign, symptom, illness, abnormal or adverse laboratory value, or experience that was not present at the start of treatment and occurs or worsens during the course of the therapy proposed regardless if related to that therapy.

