9.4 Severity of Adverse Events

Numerical grading of adverse events will follow the Common Terminology for Criteria for Adverse Events version 5.0 from the U.S. Department of Health and Human Services:

Grade 1: Mild; asymptomatic or mild symptoms; clinical or diagnostic implications only; intervention not indicated.

Grade 2: Moderate; minimal, local or noninvasive intervention indicated; limiting age-appropriate instrumental activities of daily living.

Grade 3: Severe or medically significant but not immediately life-threatening; hospitalization or prolongation of hospitalization indicated; disabling; limiting self-care activities of daily living.

Grade 4: Life-threatening consequences with urgent intervention indicated.

Grade 5: Death from AE.

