10.2 Secondary Endpoints

Secondary outcomes of our study will include the analysis of safety and toxicity, disease free survival, and overall survival from data included up to five years after enrollment in the study. Data will be stored in the RedCap database.

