10.3 Data Analysis

We aim to accrue 40 participants over approximately a 5-year period. Though we hypothesize that this study will be of clinical benefit to those who may avoid surgical intervention, we have no knowledge that a similar study has been conducted. Thus, we aim to gain a preliminary estimate of the rate of locally advanced rectal cancer patients that can be spared surgical intervention through the use of neoadjuvant chemotherapy plus short course radiation. We anticipate a 30% rate of complete or near complete clinical response to neoadjuvant chemotherapy plus short course radiation at the post-radiation assessment. This rate will include subjects discontinuing mFOLFOX due to stable or progressive disease at the interval assessment or re-staging assessment in the denominator.

With an anticipated response rate of 30%, a sample size of 40 subjects produces a one-sided 95% lower-limit exact binomial confidence interval with a width of 13.4% (lower limit of 16.6%). The maximum width of a one-sided 95% lower-limit confidence interval with 40 subjects would be 16.1% when the response rate is 50%. We target the lower limit of the confidence interval to determine if this regimen demonstrates sufficient evidence of efficacy to be considered worthy of future study.

The complete or near complete response rate and associated 95% one-sided exact binomial confidence interval will be presented. Disease-free and overall survival will be described using the Kaplan-Meier method. Types and grades of adverse events will be tabulated. Changes in QOL (from baseline) will be described using means and standard deviations at each time point assessed. We will calculate these summary measures separately in those who obtain a complete or near complete response to up to 12 cycles of mFOLFOX and short course radiation and are entering watch and wait surveillance, and those who required surgery with or without radiation therapy prior to completion of mFOLFOX therapy. QOL will be measured using validated

QOL forms EORTC QLQ-30, and EORTC QLQ-CR29 as mentioned in Section 5.2, with paper-based surveys and scored according to the EORTC scoring manual [10].

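### Sections 9.1 and 9.3 give different rules for when a laboratory abnormality is an adverse event, so the laboratory part of the safety endpoint rests on an undefined provider judgement

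*Combined protocol and SAP*

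**What the plan says.** Section 9.1 defines an adverse event as "any sign, symptom, illness, abnormal or adverse laboratory value, or experience that was not present at the start of treatment" and that occurs or worsens during therapy, whether or not therapy caused it. It sets no threshold of importance.

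Section 9.3 gives the recording procedure. The assessor is the treating provider: "With each visit, the patient provider will assess the patient for AE since prior visits". The list of items to document ends with the rule specific to laboratory results: "Laboratory values will be included as adverse events if clinically significant and included in reporting".

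Section 9.4 adopts CTCAE version 5.0 and describes grade 1 as "Mild; asymptomatic or mild symptoms; clinical or diagnostic implications only; intervention not indicated".

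Section 10.2 makes this an endpoint: "Secondary outcomes of our study will include the analysis of safety and toxicity". The whole safety analysis in section 10.3 is one sentence: "Types and grades of adverse events will be tabulated".

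**The concern.** A laboratory change can be an adverse event by the definition in 9.1 and yet be left out under 9.3. The condition that decides is not tied to a grade, an intervention, a dose change or a named adjudicator. Two providers looking at the same blood count could record it differently, and both would be following the protocol.

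This reaches the analysis because 10.3 works from recorded events alone. A value that is not recorded as an adverse event appears nowhere in the planned safety output. The AE spreadsheet sent to the Data Safety Monitoring Committee under section 11.2 comes from the same records. The trial has no control arm and describes no masking, so the people deciding what counts as toxicity know the treatment and its response results. Under-counting would make the regimen look better tolerated than the blood results show.

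**Working it through.** The plan states no laboratory event rate, so there is no figure to reproduce. The check is a comparison of the sections.

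1. **What each rule counts.** Here 9.3 is read as a condition added to 9.1.

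| Laboratory change | Section 9.1 | Section 9.3 |
|---|---|---|
| Abnormal at baseline, unchanged | Not counted | Not counted |
| New or worsened, grade 1, no symptoms | Counted | Only if judged significant; nothing guides the judgement |
| New or worsened, grade 2 | Counted | Only if judged significant; section 7.0 recommends dose modification from grade 2, so many would be |
| New or worsened, grade 3 or higher | Counted | Formally still a judgement, but 9.4 describes grade 3 in terms of severity or medical significance |

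The two rules separate most clearly at grade 1. The CTCAE wording in 9.4 treats findings without symptoms or need for intervention as gradable events, and these are the ones a provider can most easily set aside under 9.3.

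2. **Whether another section settles it.** Section 9.4 supplies grades but does not say which values become events. The only other laboratory rule, in 11.2, concerns isolated grade 4 abnormalities and decides only whether they are reportable as *serious* events. Neither says whether 9.1 or 9.3 prevails.

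3. **Whether laboratory events matter in this regimen.** Of the ten common oxaliplatin toxicities in section 8.1, three are laboratory findings (raised transaminases, anemia, thrombocytopenia). Of the eight common 5-FU toxicities in 8.3, three are (anemia, thrombocytopenia, leukopenia). Section 8.4 lists none for radiation. Laboratory findings are therefore a real part of the expected profile, but not most of it.

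4. **How often the judgement is exercised.** Tables 2 and 3 schedule CBC and CMP on day 1 of every cycle and at the interval, restaging, radiation and post-radiation columns. For a patient who has all 12 cycles, the occasions after the first dose are cycles 2 to 12 (11) plus those four: 11 + 4 = 15.

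5. **Size.** Let p be the share of treated patients with at least one new or worsened abnormality of a given type, and q the share of those patients with at least one such value judged significant. Section 9.1 gives a rate of p and section 9.3 gives p × q, so the gap is p − pq = p(1 − q). It runs from 0 when q = 1 to p when q = 0. The documents give neither p nor q, and q should rise with grade. No numerical size follows.

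**The case against.** The best defence is that there is no contradiction. Section 9.1 is the general definition. Section 9.3 is the specific rule for recording laboratory values, and a specific rule normally qualifies a general one. Filtering laboratory events by clinical significance can be reasonable. This reading is available, and it weakens the idea that sites would choose between two sections. It does not remove the problem: the filter still has no criterion, and the tabulated rates still depend on it.

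The defence also limits the point in several ways, and these limits stand.

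- Section 9.1 does not reach every abnormal value. Values already abnormal at the start and unchanged are outside it. This matters because section 4.1 admits patients with hemoglobin down to 8.0 g/dL and AST or ALT up to 2.5 times the upper limit.
- A reader might infer that grade 3 toxicity will routinely go missing. The text permits it, but 7.0 and 9.4 make it unlikely.
- A reader might infer that rates will differ between sites. Section 3.0 says "This is a multi-center, phase II study", and section 11.2 mentions participating sites, but the title page lists one site and no between-site safety comparison is planned. Variation between providers could arise at a single site.
- A reader might conclude that the rates could not be set against other FOLFOX series. The documents do not say how those studies recorded laboratory events, so this cannot be argued from them.

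**Conclusion.** The point holds and should be corrected, at moderate priority. The definition and the recording rule do not agree, nothing reconciles them, and the planned tabulation has no other source for laboratory toxicity. The likely consequence is under-counting, mainly of low-grade changes, in a descriptive secondary endpoint.

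A reader may want to put a number of percentage points on this, or to weigh it against sampling error. The documents do not support either step: any number would come from assumed values of p and q, the gap may be zero, and no planned test or threshold uses these rates.

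The conclusion assumes that 10.3 means what it says, namely that events as recorded are tabulated with no separate grading of laboratory data. The response endpoint, the sample size and the rules for serious adverse events do not depend on it.

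**What to change.** Reconcile 9.1 and 9.3 so that one rule decides which laboratory values are adverse events for analysis. Say explicitly that a value abnormal at baseline counts only if its grade worsens, since 9.1 is loosely worded on this.

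In 10.3, state that laboratory toxicity will be derived from the scheduled CBC and CMP results using CTCAE v5.0. Take the last value before the first dose as baseline, count grades that are new or worse than baseline, and tabulate the worst such grade per treated patient for each parameter. Use the collection window that section 11.1 already sets for non-serious events, from first dosing to the first surveillance safety visit. Keep clinical significance only as the trigger for an additional narrative adverse event entry.

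No extra blood draws are needed. Section 12.0 says that data extracted from the chart go into the study database, but not that every CBC and CMP value is entered, so some data entry may be required along with a little programming. Stated laboratory toxicity rates may rise; the report should say that they come from graded laboratory data.

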9.4 Severity of Adverse Events

Numerical grading of adverse events will follow the Common Terminology for Criteria for Adverse Events version 5.0 from the U.S. Department of Health and Human Services:

Grade 1: Mild; asymptomatic or mild symptoms; clinical or diagnostic implications only; intervention not indicated.

Grade 2: Moderate; minimal, local or noninvasive intervention indicated; limiting age-appropriate instrumental activities of daily living.

Grade 3: Severe or medically significant but not immediately life-threatening; hospitalization or prolongation of hospitalization indicated; disabling; limiting self-care activities of daily living.

Grade 4: Life-threatening consequences with urgent intervention indicated.

Grade 5: Death from AE.

10.0 Objectives and Data Analysis

10.1 Primary Endpoint

The primary outcome will be the rate of a complete clinical response. Response rates will be determined by the following:

- **A complete response** will consist of a digital rectal exam with normal appearing mucosa and sigmoidoscopy/proctoscopy with scarring but no nodularity or ulcerations.
- **A near complete response** will consist of digital rectal exam with smooth or minor mucosal abnormalities, and sigmoidoscopy/proctoscopy with small mucosal abnormalities, or superficial ulceration or erythematous scarring. No palpable lymph nodes but some induration/mucosal abnormalities
- **Partial response**, in our study, will be those tumors read with a $\geq 20\%$ decrease in size without obtaining near or complete response, or remaining palpable lymph nodes with partial response

- **Stable disease**, in our study, will be those tumors read with a <20% decrease in size without obtaining near or complete response, or palpable lymph nodes, no change in size on proctoscopy/sigmoidoscopy
- **Progressive disease** will be those tumors with >20% increase in size, new lesions or palpable lymph nodes.

10.2 Secondary Endpoints

Secondary outcomes of our study will include the analysis of safety and toxicity, disease free survival, and overall survival from data included up to five years after enrollment in the study. Data will be stored in the RedCap database.

10.3 Data Analysis

We aim to accrue 40 participants over approximately a 5-year period. Though we hypothesize that this study will be of clinical benefit to those who may avoid surgical intervention, we have no knowledge that a similar study has been conducted. Thus, we aim to gain a preliminary estimate of the rate of locally advanced rectal cancer patients that can be spared surgical intervention through the use of neoadjuvant chemotherapy plus short course radiation. We anticipate a 30% rate of complete or near complete clinical response to neoadjuvant chemotherapy plus short course radiation at the post-radiation assessment. This rate will include subjects discontinuing mFOLFOX due to stable or progressive disease at the interval assessment or re-staging assessment in the denominator.

With an anticipated response rate of 30%, a sample size of 40 subjects produces a one-sided 95% lower-limit exact binomial confidence interval with a width of 13.4% (lower limit of 16.6%). The maximum width of a one-sided 95% lower-limit confidence interval with 40 subjects would be 16.1% when the response rate is 50%. We target the lower limit of the confidence interval to determine if this regimen demonstrates sufficient evidence of efficacy to be considered worthy of future study.

The complete or near complete response rate and associated 95% one-sided exact binomial confidence interval will be presented. Disease-free and overall survival will be described using the Kaplan-Meier method. Types and grades of adverse events will be tabulated. Changes in QOL (from baseline) will be described using means and standard deviations at each time point assessed. We will calculate these summary measures separately in those who obtain a complete or near complete response to up to 12 cycles of mFOLFOX and short course radiation and are entering watch and wait surveillance, and those who required surgery with or without radiation therapy prior to completion of mFOLFOX therapy. QOL will be measured using validated

QOL forms EORTC QLQ-30, and EORTC QLQ-CR29 as mentioned in Section 5.2, with paper-based surveys and scored according to the EORTC scoring manual [10].

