NCT03781323

**Neoadjuvant FOLFOX therapy with Short Course Radiation and active surveillance in locally advanced
Rectal Cancer: A Phase II Study**

Version Date: 12/9/2019

Principal Investigator: [name]

Statistician: [name]

**Site: University of Rochester
James P. Wilmot Cancer Institute
[name]
[name]**

Figure 1. Schema

- Total number of patients enrolled to start chemotherapy, N=30
- All patients included in evaluation of complete clinical response, safety, toxicity, quality of life, and overall survival

[figure not shown]

Table of Contents

- 1.0 Purpose of Study and Rationale
 - 1.1 Purpose of Study
 - 1.2 Rationale
- 2.0 Study Objectives
 - 2.1 Primary Objective
 - 2.2 Secondary Objectives
- 3.0 Study Design
- 4.0 Selection Criteria
 - 4.1 Inclusion Criteria
 - 4.2 Exclusion Criteria
- 5.0 Methods and Study Procedures
 - 5.1 Subject Recruitment and Consent
 - 5.2 Pretreatment Evaluation
 - 5.3 Administration Schedule
 - 5.4 Disease Progression
 - 5.5 Posttreatment evaluation
 - 5.6 Discontinuation of Study
- 6.0 Schedule of Events
- 7.0 Treatment Dosing Modifications
- 8.0 Study Treatment Toxicities
 - 8.1 Oxaliplatin
 - 8.2 Leucovorin
 - 8.3 5-Flurouracil
- 9.0 Adverse Events Monitoring and Reporting
 - 9.1 Definition of Adverse Event
 - 9.2 Definition of Serious Adverse Event
 - 9.3 Reporting of Adverse Events
 - 9.4 Severity of Adverse Events
- 10.0 Objectives and Data Analysis
 - 10.1 Primary Endpoint
 - 10.2 Secondary Endpoints
 - 10.3 Data Analysis
- 11.0 Data Safety and Monitoring
- 12.0 Data Confidentiality and Storage
- 13.0 Data and Specimen Banking for Future Use
- 14.0 References

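### Section 10.3 gives 40 subjects the precision figures that belong to 30, and the schema says N=30: the two sample sizes must be reconciled

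*Combined protocol and SAP*

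**What the plan says.** Section 10.3 (Data Analysis) sets the accrual target: "We aim to accrue 40 participants over approximately a 5-year period". It also states the expected result: "We anticipate a 30% rate of complete or near complete clinical response". The sample size is then justified by precision alone. The text says that "a sample size of 40 subjects produces a one-sided 95% lower-limit exact binomial confidence interval with a width of 13.4% (lower limit of 16.6"%), and continues: "The maximum width of a one-sided 95% lower-limit confidence interval with 40 subjects would be 16.1% when the response rate is 50"%. The same kind of interval is planned for the report: "The complete or near complete response rate and associated 95% one-sided exact binomial confidence interval will be presented". The lower limit is given a role in judging the regimen: "We target the lower limit of the confidence interval to determine if this regimen demonstrates sufficient evidence of efficacy".

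The schema (Figure 1) has a different count: "Total number of patients enrolled to start chemotherapy, N=30". Its next line reads: "All patients included in evaluation of complete clinical response, safety, toxicity, quality of life, and overall survival".

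**The concern.** There are two faults, and they point to the same number. First, the precision figures in Section 10.3 do not follow from 40 subjects by the method that the section names. Second, the schema gives 30 where Section 10.3 gives 40, and no dropout allowance or distinction between accrued and treated patients explains the gap.

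These are the only sample-size figures in the documents, and they are the whole justification for the size of the trial. As the text stands, sites and the data safety monitoring committee, which reviews accrual, cannot tell whether enrolment ends at 30 or at 40. Nor can a reader tell which precision the trial was designed to deliver.

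**Working it through.** **Inputs.** Sample size 40 (Section 10.3) or 30 (schema). Response rate 30%, and 50% for the second width (Section 10.3). Exact binomial interval, one-sided, 95% (Section 10.3).

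**Formula.** For x responders out of n, the one-sided 95% exact (Clopper-Pearson) lower limit L is the 0.05 quantile of a Beta(x, n − x + 1) distribution. Equivalently, L is the rate at which x or more responders out of n have probability 0.05. The width is x/n − L.

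**Step 1: reproduce the printed figures with n = 40.**
- 30%: x = 12, L = 0.1831, width = 0.3000 − 0.1831 = 0.1169.
- 50%: x = 20, L = 0.3611, width = 0.5000 − 0.3611 = 0.1389.

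None of the three printed figures appears. As a direct check, if the true rate were 16.6%, the probability of 12 or more responders out of 40 would be 0.025. A one-sided 95% limit requires 0.05.

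**Step 2: the same with n = 30.**
- 30%: x = 9, L = 0.1663, width = 0.3000 − 0.1663 = 0.1337.
- 50%: x = 15, L = 0.3389, width = 0.5000 − 0.3389 = 0.1611.

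All three match to the printed decimal.

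| | Printed, labelled 40 | Computed, n = 40 | Computed, n = 30 |
|---|---|---|---|
| Lower limit at 30% | 16.6% | 18.3% | 16.6% |
| Width at 30% | 13.4% | 11.7% | 13.4% |
| Width at 50% | 16.1% | 13.9% | 16.1% |

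**Step 3: could another n fit?** I evaluated the formula for every n from 20 to 60 at x = 0.3n and x = 0.5n, allowing fractional x. Only n = 30 gives all three. The neighbours miss: n = 29 gives 16.4%, 13.6% and 16.4%, and n = 31 gives 16.8%, 13.2% and 15.8%.

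**Step 4: could another method fit n = 40?** The closest is the lower end of a two-sided 95% exact interval (0.025 quantile). At 12/40, L = 0.1656 and the width is 0.1344. At 20/40, L = 0.3380 and the width is 0.1620. Rounded, these are 16.6%, 13.4% and 16.2%. Truncated, they are 16.5%, 13.4% and 16.1%. Neither convention gives all three printed figures. Wald, continuity-corrected Wald, Wilson and Jeffreys limits at n = 40 do not give them either.

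**Step 5: size of the error if 40 is right.** At 30%, 13.4 − 11.7 = 1.7 percentage points too wide. At 50%, 16.1 − 13.9 = 2.2 points too wide. The sample sizes differ by 40 − 30 = 10 patients, a quarter of 40.

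**Step 6: is 50% where the width is largest?** No. Over all x, the one-sided exact width peaks at 14.2% for n = 40 (25/40) and at 16.6% for n = 30 (19/30). The claim of a maximum at 50% is slightly wrong for either size.

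**The case against.** The best rescue of the figures is that they come from a two-sided 95% interval at 40 subjects. It matches two of the three, and only 0.1 point at 50% separates it from the explanation by 30. That much is fair: where the figures came from is an inference, although the N=30 in the schema supports it. But Section 10.3 says one-sided three times, including for the final analysis. On this reading it would misstate its own method, and the conflict with the schema would remain.

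The best rescue of the two sample sizes is that 40 are accrued and 30 of them start chemotherapy. The wording allows it, since one place counts accrual and the other counts patients starting treatment. But a pre-treatment loss of one quarter is stated nowhere, and Section 10.3 attaches the interval to 40 subjects. Under this reading the interval would still have to be attached to 30.

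The practical weight can also be disputed. The plan has no hypothesis test and no numerical pass mark, it calls its aim a preliminary estimate, and the reported interval will be computed from observed data. If 40 stands, the printed precision is conservative. All of this is true. It limits the harm done by the wrong percentages but does not settle how many patients are to be enrolled.

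**Conclusion.** The concern holds and must be corrected. By the stated one-sided 95% exact method, the lower limit of 16.6% and the widths of 13.4% and 16.1% belong to 30 subjects. For 40 they should be 18.3%, 11.7% and 13.9%. The schema and Section 10.3 differ by ten patients, and the documents do not show which size is intended.

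If 40 is right, the schema and the three percentages are wrong, and the trial is somewhat more precise than stated. If 30 is right, the percentages stand, and the accrual target and both sample-size sentences are wrong. The seriousness rests on the unresolved enrolment number more than on the percentages. The 16.6% is the limit expected if 30% respond and is not a decision threshold, so the planned analysis is unaffected.

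The arithmetic assumes only what Section 10.3 states: an exact binomial limit, one-sided, at 95%, with observed rates of exactly 30% and 50%.

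**What to change.** Choose one N and make the schema and Section 10.3 agree.

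- **If 40:** change the schema to N=40. In Section 10.3, state that 40 subjects give a one-sided 95% exact lower limit of 18.3% (width 11.7%) at a 30% response rate and a width of 13.9% at 50%.
- **If 30:** change all three mentions of 40 in Section 10.3 (the accrual target and both sample-size sentences) to 30, and keep the printed percentages.
- **If 40 are to be accrued and 30 to start chemotherapy:** state both numbers, explain the expected loss, and attach the interval to 30.

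In every case, stop describing the 50% width as the maximum.

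A secondary point, on which the severity does not rest: since the lower limit is to show whether efficacy is sufficient, the sponsor should name the value it must exceed and the matching responder count. The documents imply no particular value. As assumed examples only, a limit above 10%, 15% or 20% needs at least 8, 11 or 13 responders out of 40, or 7, 9 or 11 out of 30.

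The cost is wording in two places. Choosing 40 adds no patients relative to Section 10.3 and ten relative to the schema. Choosing 30 adds none.

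### Section 10.3 gives 16.1% at a 50% response rate as the maximum width of the one-sided exact interval with 40 subjects; both the value and the location are wrong

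*Combined protocol and SAP*

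**What the plan says.** Section 10.3 (Data Analysis) sets the size of the study: "We aim to accrue 40 participants over approximately a 5-year period". It justifies that size by the precision of an exact binomial interval and names no hypothesis test. For the anticipated rate it says that "a sample size of 40 subjects produces a one-sided 95% lower-limit exact binomial confidence interval with a width of 13.4% (lower limit of 16.6" per cent). The worst case follows: "The maximum width of a one-sided 95% lower-limit confidence interval with 40 subjects would be 16.1% when the response rate is 50" per cent. The rate used for planning is also given there: "We anticipate a 30% rate of complete or near complete clinical response to neoadjuvant chemotherapy plus short course radiation at the post-radiation assessment".

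The section then says what the limit is for, namely to decide whether the regimen merits another trial: "We target the lower limit of the confidence interval to determine if this regimen demonstrates sufficient evidence of efficacy to be considered worthy of future" […]. It gives no numerical threshold for that limit.

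Figure 1 (Schema), at the front of the same document, gives another size: "Total number of patients enrolled to start chemotherapy, N=30".

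**The concern.** Width here means the observed rate minus the lower confidence limit. The plan treats this width as largest at 50%. That is true of a normal-approximation (Wald) half-width and of the total width of a two-sided exact interval. It is not true of the lower arm of an exact interval taken alone. The spread that fixes the exact lower limit is the binomial spread at the limit itself, not at the estimate, so the arm is longest when the limit lies near 50%. The estimate is then above 50%.

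The sentence therefore carries two errors: the value does not belong to 40 subjects, and the location is wrong for any sample size considered. Correcting only the sample size would give 13.9% at 50% and still call it the maximum. What is at stake is modest. The design rests on interval width and the lower limit is the quantity used to judge the regimen, so a stated bound on that width should be true.

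**Working it through.** **Inputs.** N = 40 (section 10.3) and N = 30 (Figure 1). One-sided 95% exact lower limit, so 0.05 in one tail (section 10.3). Anticipated rate 30%; stated maximum 16.1% at 50% (section 10.3).

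**Formula.** For x responders among N, the exact (Clopper-Pearson) lower limit L solves P(X ≥ x | N, L) = 0.05. Equivalently, L is the 0.05 quantile of a Beta(x, N − x + 1) distribution. Width = x/N − L.

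**Step 1: reproduce the plan's figures.**

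| Quantity | Plan, stated for 40 | Recomputed, N = 40 | Recomputed, N = 30 |
|---|---|---|---|
| Lower limit at 30% | 16.6% | 18.3% (12/40) | 16.6% (9/30) |
| Width at 30% | 13.4% | 11.7% | 13.4% |
| Width at 50% | 16.1% | 13.9% (20/40) | 16.1% (15/30) |

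None of the three printed figures reproduces at N = 40. All three reproduce at N = 30.

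**Step 2: find the maximum by evaluating every x from 0 to N.**

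| N | x | Rate | Lower limit | Width |
|---|---|---|---|---|
| 40 | 20 | 50.0% | 36.11% | 13.89% |
| 40 | 24 | 60.0% | 45.78% | 14.22% |
| 40 | **25** | **62.5%** | **48.28%** | **14.22%** |
| 40 | 26 | 65.0% | 50.81% | 14.19% |
| 30 | 15 | 50.0% | 33.89% | 16.11% |
| 30 | 18 | 60.0% | 43.39% | 16.61% |
| 30 | **19** | **63.3%** | **46.69%** | **16.64%** |
| 30 | 20 | 66.7% | 50.06% | 16.61% |

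At N = 40, 24 and 25 responders agree to two decimals; to three they are 14.222% and 14.225%, so the maximum is at 25. Every outcome from 21 to 28 responders is wider than 20/40. At N = 30, every outcome from 16 to 22 is wider than 15/30. In both cases the lower limit at the peak is close to 50%, as the reasoning about asymmetry predicts.

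**Step 3: size of the error.**

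- Printed figure against the true maximum, N = 40: 16.1 − 14.2 = 1.9 points too high.
- Printed figure against the true maximum, N = 30: 16.6 − 16.1 = 0.5 points too low.
- Peak location alone (maximum minus width at 50%): 14.22 − 13.89 = 0.33 points at N = 40; 16.64 − 16.11 = 0.53 points at N = 30.

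**Step 4: other readings at N = 40.**

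| Method | Width at 50% | Where it peaks |
|---|---|---|
| Exact, 0.025 in the lower tail | 16.2% | 16.7% at 62.5% |
| Wald | 13.0% | 50% |
| Wald, continuity-corrected | 14.3% | 50% |
| Wilson | 12.6% | 13.0% at 62.5% |
| Jeffreys | 12.7% | not evaluated |

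The 0.025 tail comes closest: it gives 13.4% and a lower limit of 16.6% at a 30% rate, but 16.2% at 50%, and its maximum is again above 50%. No reading gives a maximum of 16.1% at 50% with 40 subjects.

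**The case against.** The strongest objection is that this has no practical consequence. The plan anticipates 30%, and section 1.2 puts the likely complete response rate at 30 to 40%. The peak, near 63%, is about twice the planning rate. With 40 subjects the width is 11.7% at 30% and 13.1% at 40%, wherever the curve peaks. No sample size or decision threshold is derived from the maximum, and the interval reported at the end will be computed at the observed rate. All of this stands, and it limits the weight of the point.

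A second objection is that the larger fault in the sentence is the sample size: the figures fit 30 while the text says 40. That also stands. The two corrections touch the same words and should be made together. It does not make this point redundant, because a correction of the sample size alone would leave a false maximum.

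A third is that the sentence does not repeat the word exact, and a Wald half-width does peak at 50%. This does not rescue it. The preceding sentence specifies the exact interval, as does the planned analysis, and Wald gives 13.0% at N = 40 and 15.0% at N = 30, not 16.1%.

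A reader might go further and infer that the plan understates its worst-case uncertainty at either sample size, or that the study is too small. The documents do not support either inference. For the 40 subjects named, the printed 16.1% is larger than the true maximum of 14.2%, so it errs on the cautious side; understatement arises only if 30 is the intended size. The 13.9% that a partial correction would give appears nowhere in the plan, so the gap of 0.3 points is not an error in the sentence as printed.

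**Conclusion.** The sentence is wrong as written, in value and in location. With 40 subjects the maximum width is 14.2% at a 62.5% response rate, against a printed 16.1% at 50%: too high by 1.9 points. With 30 subjects the maximum is 16.6% at 63.3%: the printed figure is too low by 0.5 points.

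This is a minor correction of a stated precision figure, not a design defect. It rests on three assumptions: the interval is the exact one-sided 95% limit that section 10.3 specifies, width means the estimate minus that limit (the plan's own use, since 30 − 16.6 = 13.4), and the denominator is the full 40 or 30. Which size is intended cannot be settled from the documents. The location is wrong under either.

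**What to change.** Confirm the sample size first, since section 10.3 and Figure 1 disagree, and recompute all the precision figures in section 10.3 for it. Then restate the worst case in one of two ways:

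- Give the true maximum: 14.2% at a response rate of 62.5% for N = 40, or 16.6% at 63.3% for N = 30.
- Drop the claim of a maximum and give the width at 50%: 13.9% for N = 40, or 16.1% for N = 30.

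The cost is one sentence, within an edit that the sample-size mismatch already requires. At N = 40 either option is more favourable than what is printed. At N = 30 the true maximum is slightly less favourable, and the second option keeps the printed number while removing the false description. The sample size and the planned analysis stay as they are.
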